Martin [22]	2013	RCT	-	57	Ø (32)	43.8% ¹	Fibrin glue: TISSEEL (59)	40% ¹	NS

1- Fistula grade A, B & C; 2- Fistula grade B & C

Hemopatch is an NHS-PEG patch that consists of a soft, thin, pliable, flexible pad of collagen derived from bovine dermis, coated with NHS-PEG (pentaerythritol polyethylene glycol ether tetra-succinimidyl glutarate). It is intended as a surgical sealant for procedures in which control of leakage by conventional surgical techniques is either ineffective or impractical [23], making it a plausible option to use during PD surgical technique in order to decrease POPF.

Preliminary experience with Hemopatch: case serie

In our center we have been using this NHS-PEG patch envolving the pancreaticojejunostomy as a new way to decrease POPF after PD. The results of more than a year of experience have been submitted as an abstract communication to the E-AHPBA congress in Mainz, Germany (May, 2017), and are the following:

Sealing with NHS-PEG patch to prevent postoperative pancreatic fistula after pancreaticojejunostomy

[name], [name], [name], [name], [name]

Background. Postoperative pancreatic fistula (POPF) is a common and most severe complication following pancreaticoduodenectomy (PD) (9.8% to 34.2%). POPF not only prolongs hospital stay and increases healthcare costs, but also plays a central role in the development of life-threatening events such as intra-abdominal abscess and

*Study protocol - Use of Hemopatch as a sealant in pancreaticojejunostomy after PD.
Version 2.0.*

postoperative hemorrhage. We present a new way to decrease POPF after PD using a NHS-PEG patch envolving duct-to-mucosa (DTM) pancreaticojejunostomy.

Materials and methods. 26 consecutive PD were performed from July 2015 to October 2016, using the same technique, 13 of them sealing with NHS-PEG patch after DTM. Both groups were statistically homogeneous. Demographic data were collected (age, gender, diagnosis, date of intervention), and rates of postoperative complications (pancreatic fistula, biliary fistula, delayed gastric emptying –DGE-, hemorrhage, exitus, Clavien-Dindo classification, readmission and mean stay).

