Results. Postoperative complication rates were (with NHS-PEG patch/without NHS-PEG patch): pancreatic fistula (A: 7.7%/7.7%; B: 0%/7.7%; C: 0%/15.5%); biliary fistula: 7.7%/15.4%; DGE: 7.7%/7.7%; hemorrhage: 7.7%/15.5%; exitus: 0%/7.7%; readmission: 7.7%/46%; mean stay: 21.3/26.1 days; other complications: 61.5%/46.2%.

Discussion. Sealing with NHS-PEG patch to prevent postoperative pancreatic fistula after DTM pancreaticojejunostomy can offer a new possibility to decrease POPF, with less fistula rate B and C, less hospital stay an less healthcare costs. Randomized controlled trials with larger number of patients should be performed to support this theory.

Therefore, we have design the following randomized controlled trial in order to validate our positive experience with Hemopatch in PD.

5. HYPOTHESIS / OBJECTIVE.

This unicentric, double-blind, randomized study investigates the efficacy and tolerance of Hemopatch in the prevention of POPF type B and C after a PD. The goal for Hemopatch is to reduce the risk of POPF type B and C from 30% to 15%.

6. STUDY DESIGN.

6.1. Type of study.

Unicentric, randomized, controlled, double-blind, prospective study with a parallel design of two groups. After giving informed consent, patients will not know to which group they have been assigned (reinforcement with Hemopatch or not). After the last follow-up visit on postoperative day 30, the patients can receive this information if they wish.

This study is also blind on the part of the observer; the final result will be determined by an independent observer, making this a double-blind study.

6.2. Primary objective and secondary objectives.

Primary endpoint: POPF type B and C, according to the definition of the ISGPF (Bassi, Surgery 2005), that is, the secretion of pancreatic fluid externalized through a drain or removed during a reoperation, independently of the color and / or appearance on day 3 or later, whose amylase is 3 times the values of serum amylase or collections (infected or not) detected by fistulography or other imaging techniques (computed tomography, ultrasound, magnetic resonance imaging). See attached table.

Grade	A	B	C
Clinical conditions	Well	Often well	Ill appearing / bad
Specific treatment*	No	Yes / no	Yes
US / CT (if obtained)	Negative	Negative / positive	Positive
Persistent drainage (after 3 weeks)**	No	Usually yes	Yes
Reoperation	No	No	Yes
Death related to POPF	No	No	Possibly yes
Signs of infections	No	Yes	Yes
Sepsis	No	No	Yes

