- The investigator suspects a serious threat to the patient's well-being. Adverse events (any sign or symptom that affects the patient's well-being) and serious adverse events (life-threatening, prolongs hospital stay, results in persistent disability or leads to death during the observation period), as cardiopulmonary problems, in the gastrointestinal tract, anaphylactic shock or embolism will be recorded through daily postoperative visits until discharge and during the final visit on the 30th postoperative day. All adverse effects of clinical relevance and all serious adverse effects will be recorded in the case report form along with the degree of the complication (according to the Clavien-Dindo classification). The principal investigator must be informed within 24 hours about the serious adverse effects that occur during the hospital stay. The presence of a causal relationship between adverse effect or serious adverse effect and the intervention of the trial will be judged by the investigator. Serious adverse effects will be reported immediately (ie, within 5 days after recognition) by all investigators to the coordinating investigator. The coordinating researcher must inform the responsible ethics committee and the research sponsor. A list of all serious adverse effects must be compiled.

8. DATA.

8.1. Calculation of the sample size.

The sample size was calculated by comparing two proportions, with a level of statistical significance of 5% (alpha) and a statistical power of 80% (1-beta), and taking into account the preliminary data obtained regarding the rate of POPF in the two groups: 23% for the control group, and 7% for the Hemopatch group.

With these assumptions, it will take 57 patients to detect, with an 80% probability and a level of significance of 5%, a decrease of the POPF rate of 23% in the control group to 7% in the experimental group (Hemopatch). Considering an expected proportion of losses of 10%, the sample size will be 64 patients.

8.2. Randomization and groups.

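### The 23% and 7% planning rates match no single fistula definition in the pilot, and 57 patients with 80% power does not follow from them

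*Combined protocol and SAP*

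**What the plan says.** - **Endpoint (section 6.2).** "Primary endpoint: POPF type B and C, according to the definition of the ISGPF". Grade A fistula is not an event.
- **Planning rates (section 8.1).** The calculation was made "taking into account the preliminary data obtained regarding the rate of POPF in the two groups", which are given as "23% for the control group, and 7% for the Hemopatch group". No grade is named. Alpha is 5%, with sidedness not stated, and power is 80%. The result is 57 patients, raised to 64 for 10% losses; section 8.2 splits these as 32 per group.
- **Pilot (Preliminary experience with Hemopatch).** There were 26 consecutive operations, "13 of them sealing with NHS-PEG patch after DTM". The results, in the order with patch / without patch, were "pancreatic fistula (A: 7.7%/7.7%; B: 0%/7.7%; C: 0%/15.5"%.
- **Goal (section 5, repeated in section 10).** "The goal for Hemopatch is to reduce the risk of POPF type B and C from 30% to 15"%.
- **Test (section 8.5).** Chi-square with Yates correction, with an odds ratio from logistic regression.

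**The concern.** Section 8.1 offers its two rates as observed preliminary data, yet the only preliminary series the document reports does not contain them as a pair. The control figure agrees with the pilot's B/C rate. The Hemopatch figure does not, because that arm had no B/C fistula. A reader checking the basis of the sample size cannot tell which endpoint, or which effect, the 80% refers to.

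The second difficulty is independent of the first. Taking 23% and 7% at face value, 57 patients in total is far too few for 80% power. An ethics committee or a reader of the results who relied on section 8.1 would credit the trial with a sensitivity it lacks, and could read a null result as stronger evidence against a benefit than it is. Sections 5 and 10 add a third B/C pair, 30% and 15%, for which the power is lower still.

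**Working it through.** **1. Pilot rates by definition (13 per arm)**

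| Definition | Without patch | With patch |
|---|---|---|
| B/C (primary endpoint) | 1 + 2 = 3/13 = 23% | 0/13 = 0% |
| Grade A | 1/13 = 7.7% | 1/13 = 7.7% |
| Any grade | 4/13 = 31% | 1/13 = 8% |

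No row gives 23% against 7%. The nearest Hemopatch figure is 7.7%, which is all grade A and, in that arm, is also the any-grade rate.

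**2. The plan's own figure**

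The loss adjustment is right: 57/0.9 = 63.3, so 64. That also shows that 57 is used as a total. To reproduce 57 from 23% and 7%, I used the pooled-variance formula, with p̄ the mean of the two rates and d their difference:

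n per arm = [z_α √(2p̄(1−p̄)) + z_β √(p₁(1−p₁) + p₂(1−p₂))]² / d²

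Two-sided 5% (z_α = 1.960), 80% power (z_β = 0.8416), p̄ = 0.15, d = 0.16:

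- 1.960 × √0.255 = 0.9897
- 0.8416 × √0.2422 = 0.4142
- (0.9897 + 0.4142)² / 0.0256 = 76.99, so **77 per arm, 154 in total**

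Other two-sided versions: unpooled 75 per arm, arcsine 73, continuity-corrected 90. One-sided: pooled 60.5, unpooled 58.5 and arcsine 57.2 per arm before rounding up, or about 57 to 61; continuity-corrected 73. No version gives 57 as a total.

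**3. Same formula, other pairs (two-sided)**

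- 23% vs 0%: (0.8843 + 0.3542)² / 0.0529 = 28.99, so 29 per arm, 58 in total
- 31% vs 8% (4/13 vs 1/13): 45 per arm, 90 in total
- 30% vs 15%: (1.1575 + 0.4889)² / 0.0225 = 120.5, so 121 per arm, 242 in total

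**4. Power of the planned size**

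Normal approximation: power = Φ{[d√n − 1.960√(2p̄(1−p̄))] / √(p₁(1−p₁) + p₂(1−p₂))}. For 23% vs 7% at n = 32 this is Φ[(0.9051 − 0.9897)/0.4921] = Φ(−0.172) = 0.43. The Yates column sums the binomial probabilities of every 2×2 table whose corrected chi-square reaches the 5% critical value.

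| True rates | n per arm | Normal approx. | Yates, exact |
|---|---|---|---|
| 23% vs 7% | 32 | 43% | 30% |
| 23% vs 7% | 28.5 (57 evaluable) | 39% | 23–24% (equal arms of 28 or 29) |
| 30% vs 15% | 32 | 30% | 20% |
| 23% vs 0% | 32 | 84% | 78% |

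The rows at 32 assume no losses. An uneven 28/29 split of the 57 gives exact Yates power of about 23% or 27%, depending on which arm has the extra patient.

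**5. Precision of the pilot**

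Exact 95% intervals: 0/13, 0 to 25% (upper limit 1 − 0.025^(1/13) = 0.247); 3/13, 5 to 54%.

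**The case against.** The strongest defence is that 7% was a deliberate, cautious choice. Zero events in 13 is not a credible planning rate, section 8.1 says only that the preliminary data were taken into account, and 7.7% would round to 8%, not 7%. Unreported later data are also possible. This stands as far as origin goes. A reader might infer that the grade A rate was put in by mistake, but the document does not say so, and in the Hemopatch arm grade A and any grade are the same number. The defence does not rescue the text, which presents 7% as a preliminary result and gives no other source. Nor does it help that section 8.1 says fistula without a grade: on an any-grade reading the control rate would be 31%, not 23%.

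A reader might also infer that 57 was really computed from 23% vs 0%, because that pair needs 58. The match misses by one, and 58 allowing for 10% losses gives 65 (58/0.9 = 64.4) or 33 per arm, not 64. A rival explanation fits at least as well: the one-sided arcsine formula gives 57.2 per arm for the written rates, so 57 could be a per-group figure used as a total. Neither can be established.

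The third tempting reading is that mixing definitions made the trial too small. It did not: the consistent B/C pair needs fewer patients (58) than the written pair (154).

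A one-sided test would help the plan somewhat, but power for 23% vs 7% at 32 per arm would still be only 56% by normal approximation, and the chi-square test in section 8.5 is not directional.

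**Conclusion.** Two faults in section 8.1 hold. First, 23% and 7% are described as preliminary data, but the reported pilot gives 23% vs 0% for the primary endpoint and 31% vs 8% for any grade. Second, the claim of 80% power with 57 patients is wrong for the rates written. The design has about 43% power at 32 per arm, or about 30% with the planned test, and less after the expected losses. Against the 30% to 15% goal it has about 30%, or 20% with the planned test. The shortfall comes from 57 not following from 23% vs 7%, and from the conflict with the stated goal.

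These figures rest on 1:1 allocation, a two-sided 5% level and the stated rates being true. They do not support saying that the trial cannot detect an effect: power of 20 to 43% is low, not nil, and if the true rates were 23% and 0% the planned test would have 78% power. That last figure is not a safe defence, since 0/13 is compatible with a true rate of up to 25%.

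**What to change.** In section 8.1:

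1. Report the pilot's B/C counts as 3/13 without and 0/13 with the patch.
2. Give the source of 7%, or present it as an assumption and not as preliminary data.
3. Name one planning pair for B/C fistula and reconcile it with the 30% to 15% goal in sections 5 and 10.
4. State whether the 5% level is one- or two-sided.
5. Replace the 80% claim with the power that 32 per arm, and 57 evaluable patients, give for the chosen pair under the Yates chi-square.

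This costs some wording and one recalculation. No extra patients are needed to make the statement true; the price is a less favourable stated power, and a null result should then be interpreted with that power and a confidence interval in view.

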Statistic analysis	For the evaluation of the primary endpoint patients will be dichotomized by the presence or absence of the sealant reinforcement. Further, patients will be categorized by the type of pancreatic fistula rate defined according to the International Study Group of Pancreatic Fistula (ISGPF). Next, a contingency table will be created to calculate positive predictive value, specificity, sensitivity, and c-index. Association between sealant reinforcement and POPF rate will be expressed as odds ratio calculated by logistic regression models with the appropriate covariates. The strength of association between categorical variables will be tested with a chi-square test with Yate's correction. Secondary end points will be analyzed descriptively by tabulation. Chi-square tests will be used to test associations among categorical variables, while Student's t-test or Mann-Whitney U-test will be used to compare continuous normal or non-normal data, respectively. Time dependent variables will be tested by Kaplan-Meier analysis and Cox regression. Statistical analysis will be performed with R.
Sample size	64 patients, 32 in each group
Ethical approval	This study is approved by the Clinical Research Ethics Committee of Aragon (CEICA)
Duration of the study	The study will begin on February 1, 2018. It is estimated a duration of 1.5 years, according to the PD rate of our center (40-50 year). Estimated end date: July 31, 2019.
Participating centers	Division of Hepato-Pancreato-Biliary Surgery, Department of Surgery, Miguel Servet University Hospital

2. PATIENT VISIT AND EVALUATION.

There will be a first visit in an outpatient clinic where the patient will be informed about the study in detail and will be offered to participate in it as long as it meets the selection criteria. Two copies of the informed consent will be signed, one of them for the patient and the other will be kept together with the study documentation. A first evaluation of the patient will be carried out as it appears in the data collection notebook.

3. STRUCTURE OF THE ORGANIZATION.

3.1. Sponsor.

Investigator Initiated Research Grant from Baxter S.L., Chicago, Illinois, United States, convened on March 24, 2017.

3.2. Principal investigators.

Principal investigator:

[name], FACS
Associate Professor at University of Zaragoza
Attending Surgeon in General Surgery
Division of Hepato-Pancreato-Biliary Surgery
Miguel Servet University Hospital
[name]

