All patient data are anonymous. Each patient who meets the selection criteria and has signed the informed consent will be entered into a database and identified by a number (from 1 to 64). The list of patient identification numbers will be in the hands of the principal investigator. After carrying out the surgery, the patient number is entered into an online computerized randomization tool ("Randomizer for clinical trials"), <https://www.meduniwien.ac.at/randomizer>. It is a tool of the University of Vienna in Austria, where the study is registered, which allows, once the patient number is entered, the randomization of the same, obtaining one of the two methods to compare, as explained in Section 7.4. (32 patients in each study group):

- Basic treatment: duct-to-mucosa pancreaticojejunostomy WITHOUT Hemopatch reinforcement.
- The same, but reinforced WITH Hemopatch.

Once the treatment to be performed is obtained, surgery will be carried out according to the treatment obtained in the randomization.

8.3. Efficacy assessments (that is, data that must be collected).

- Daily drainage debit.
- Concentration of amylase and lipase from the drainage fluid (days 3, 5 and 7 postoperatively) and every 2 days in case of permanent fistula.
- Number of postoperative days with drainage (minimum 7 days). If the amylase / lipase content of the drainage on the 7th postoperative day is within normal limits, it may be withdrawn.
- Body temperature, VAS pain score, leukocyte count and CRP.
- Duration of the stay in the ICU.
- Duration of the total hospital stay.
- Reinterventions, including percutaneous drainage of collections.
- Re-entry.
- Degree of complications according to the Clavien-Dindo classification, including both complications derived from surgery (delay of gastric emptying, bleeding, biliary fistula, wound infection, intra-abdominal

abscess, etc.) and general (atelectasis, pneumonia, urine infection, thromboembolism, etc.)

8.4. Patient data sheet.

It contains patient information including personal history (ie, smoking, diabetes, BMI), preoperative and postoperative data, intraoperative incidents, special treatment details, complications and adverse events such as new onset diabetes, pneumonia or heart problems.

All the data are collected in a central database.

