All study personnel must sign a confidentiality agreement that covers all aspects of the study and its data. The study directors will take particular responsibility for the security of the data, the documents of origin and the information about the patients.

The coordinator of the main study is also responsible for continuing education in Good Clinical Practices (GCP) in accordance with the Declaration of Helsinki.

8.5. Statistical methods and data analysis.

For the evaluation of the primary objective, patients will be dichotomized by the presence or absence of the sealant reinforcement. In addition, patients will be classified by the type of pancreatic fistula defined according to the ISGPF. Next, a contingency table will be created to calculate the positive predictive value, specificity, sensitivity and the c-index. The association between sealant reinforcement and pancreatic fistula rate will be expressed as an odds ratio calculated by logistic regression models with the appropriate covariates. The strength of association between the categorical variables will be tested with a chi-square test with the Yate correction.

Secondary objectives will be analyzed descriptively by tabulation. Chi-square tests will be used to test associations between categorical variables, while Student's t-test or Mann-Whitney U-test will be used to compare normal or non-normal data, respectively. Time-dependent variables will be tested by Kaplan-Meier analysis and Cox regression. The statistical analysis will be carried out with R.

9. PATIENT SAFETY.

A monitoring team will receive all patient data electronically including expected and unexpected events and side effects for all patients in the study. All patient data are analyzed to detect any unusual pattern. There will be permanent contact with the main coordinator of the study and will meet face to face three times a year to evaluate the course of the study based on the data collected.

10. IMPACT ON CLINICAL PRACTICE.

Hemopatch is expected to reduce the risk of postoperative type B and C pancreatic fistula from 30% to 15%, so that the number of patients currently requiring readmission with possible surgeries and interventional radiological procedures is halved. This implies not only clinical but also economic advantages, since a pancreatic fistula can double the cost of hospital treatment.

11. ETHICS AND LEGAL REQUIREMENTS.

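### Section 8.1 claims 80% power for 23% versus 7% with 57 patients (64 with losses), but 32 per group gives about 30% to 46% two-sided.

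*Combined protocol and SAP*

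**What the plan says.** Section 8.1 (Calculation of the sample size) compares two proportions at 5% significance and 80% power. It takes fistula rates of 23% (control) and 7% (Hemopatch) from the preliminary data. It concludes that "it will take 57 patients to detect, with an 80% probability and a level of significance of 5" per cent, and continues: "Considering an expected proportion of losses of 10%, the sample size will be 64 patients". It gives neither the sidedness nor the formula, and does not itself say whether 57 is a total or a per-group number.

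The rest of the protocol uses 64 as the total. The synopsis has "64 patients, 32 in each group". Section 8.2 numbers patients from 1 to 64, with "32 patients in each study group".

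Section 8.5 names the test for categorical variables: "The strength of association between the categorical variables will be tested with a chi-square test with the Yate correction". It also plans an odds ratio from logistic regression with covariates that it does not list.

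The pilot results (Preliminary experience with Hemopatch, 13 patients per group), given as with/without patch, are "pancreatic fistula (A: 7.7%/7.7%; B: 0%/7.7%; C: 0%/15.5" per cent.

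**The concern.** A fall from 23% to 7% is a 16-point difference between fairly low rates. At 32 per group it means about 7 events against 2 (32 × 0.23 = 7.4; 32 × 0.07 = 2.2). So few events rarely give 80% power.

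The 80% figure is what justifies the trial's size to the ethics committee, the sponsor and readers. If true power is below one half, the likeliest outcome is a non-significant result even when the patch works as assumed. That result could then be read as evidence against benefit from an adequately powered trial, which it would not be.

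**Working it through.** **Inputs.** p₁ = 0.23, p₂ = 0.07, alpha 0.05, power 0.80 and 10% losses (section 8.1); 1:1 allocation, 32 per group (synopsis, section 8.2). Sidedness is not stated, so both are shown. Normal quantiles: 1.960 (two-sided) or 1.645 (one-sided) for alpha, and 0.842 for power.

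**Step 1: the plan's own figures.** The loss step reproduces: 57/0.9 = 63.3, rounded up to 64. Since 64 is the trial total, 57 is being used as a total. The 57 itself does not reproduce.

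**Step 2: required n per group.** With d = 0.16, mean rate 0.15, and V = 0.23×0.77 + 0.07×0.93 = 0.2422:

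- Unpooled: n = (z_α + z_β)² V / d². Two-sided: 2.802² × 0.2422 / 0.0256 = 74.3.
- Pooled: n = [z_α √(2×0.15×0.85) + z_β √V]² / d². Two-sided: (0.9897 + 0.4142)² / 0.0256 = 77.0.
- Arcsine: n = 2(z_α + z_β)² / h², with h = 2 arcsin√0.23 − 2 arcsin√0.07 = 0.465. Two-sided: 72.7.
- Continuity-corrected: (n/4)[1 + √(1 + 4/(n d))]², with n the pooled value. Two-sided: 89.1.

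| Method | Two-sided, per group (total) | One-sided, per group (total) |
|---|---|---|
| Arcsine | 72.65 → 73 (146) | 57.23 → 58 (116) |
| Unpooled | 74.26 → 75 (150) | 58.49 → 59 (118) |
| Pooled | 76.99 → 77 (154) | 60.53 → 61 (122) |
| Continuity-corrected | 89.05 → 90 (180) | 72.49 → 73 (146) |

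The smallest total, 116, is about twice 57. Exact calculation agrees: the smallest equal groups with at least 80% power are 74 (uncorrected) and 86 (Yates) two-sided, and 58 and 71 one-sided.

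**Step 3: power delivered.** Exact power is the sum of Bin(x; n₁, 0.23) × Bin(y; n₂, 0.07) over all tables (x, y) that the test rejects. The critical chi-square is 3.841 two-sided. One-sided it is 2.706, with the higher rate in the control group.

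| Control/patch | Two-sided uncorrected | Two-sided Yates | One-sided uncorrected | One-sided Yates |
|---|---|---|---|---|
| 32/32 | 45.6% | 29.5% | 60.2% | 41.4% |
| 28/29 | 40.8% | 27.3% | 54.1% | 39.5% |
| 29/28 | 43.2% | 22.7% | 55.0% | 37.2% |

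**Step 4: precision.** The 95% half-width for the risk difference is 1.96 √(0.23×0.77/n₁ + 0.07×0.93/n₂). This is 0.171 at 32/32 and 0.180 to 0.181 at 57 evaluable, against an assumed difference of 0.16.

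**Step 5: illustration.** The table closest to the assumption at 32 per group is 7/32 versus 2/32 (22% versus 6%). The difference is 15.6 points, 95% CI −1.0 to 32.2, with p = 0.072 uncorrected and p = 0.150 with Yates.

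**Step 6: where 57 might come from.** Two results come close; neither can be proved from the documents.

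- The one-sided arcsine figure for 23% versus 7% is 57.2, but per group. Even 57 per group gives exact two-sided power of only 69% uncorrected or 59% with Yates.
- The pilot grade B/C rates are about 23% (7.7 + 15.5; 3/13) versus 0%. The two-sided pooled formula then gives 28.9 per group, about 58 in total. But section 8.1 states 7%, not 0%.

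**The case against.** **Sidedness is unstated, so a one-sided test may have been meant.** This does not rescue the figure: one-sided power at 32 per group is 60% at most.

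**The documents settle that 57 is a total.** Taken together they do: 57/0.9 rounds up to 64, and 64 is split 32/32. What remains open is whether the calculation produced 57 as a per-group number that was then used as a total.

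**The uncorrected chi-square is not the named test.** This stands in part. Section 8.5 names the Yates correction, so 30% is the figure for the test as written. The uncorrected 46% stands beside it because section 8.5 also plans a logistic odds ratio, whose adjusted power was not computed. The uncorrected test is also slightly liberal here (type I error 5.6% at a common rate of 10%).

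**The after-loss range assumes near-equal losses.** This stands as a qualification. With 57 evaluable split 31 control/26 patch, power is 19.9% (Yates) or 39.8% (uncorrected), still far below 80%.

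**The worked example is fragile.** It is an illustration only. With one event moved, 8/32 versus 2/32 gives p = 0.039 and 7/32 versus 1/32 gives p = 0.023 uncorrected; with Yates both remain non-significant (0.085 and 0.059).

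**Sections 5 and 10 give a different target, 30% to 15%.** This is a separate inconsistency, and it lowers power further: 20% (Yates) to 30% (uncorrected), two-sided, at 32 per group.

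**Conclusion.** The concern holds. The 80% power statement is wrong as written for 23% versus 7% with 57 or 64 patients in total, under every formula and either sidedness tried. The shortfall is large: the two-sided designs tried need 146 to 180 evaluable patients, and even the smallest one-sided design needs 116.

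The power figures take the 23% and 7% rates at face value and use an unadjusted comparison. The after-loss figures also assume losses split almost evenly. The two-sided reading is an assumption, because section 8.1 is silent. The origin of 57 remains undetermined, and the conclusion does not depend on it.

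**What to change.** Correct section 8.1 and carry the corrected statement into the synopsis sample-size row.

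1. The sponsor should check how 57 was obtained. Section 8.1 should then state the sidedness, the formula, the rates and fistula grades used, and whether the calculated number was per group or total. If the calculation cannot be recovered, say so.
2. Replace the 80% statement with what 64 patients deliver for 23% versus 7%, labelled by test. Two-sided, with all 64 evaluable: about 30% (Yates) or 46% (uncorrected). After 10% losses split almost evenly: about 23–27% or 41–43%. Add the 95% half-width of about 17 points, or 18 after losses. If a one-sided test is confirmed, give those powers instead: 41% (Yates) or 60% (uncorrected) at 32/32, and 37–40% or 54–55% after losses.
3. Report the primary result with its confidence interval, so that a non-significant finding is not presented as coming from a trial with 80% power.

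The cost is a change of wording in two places and one check of the original calculation. The correction itself needs no extra patients; whether to revisit the sample size is a separate design decision. The price is a less favourable stated power. The new sentence should also be reconciled with the 30% to 15% target in sections 5 and 10, so that the protocol does not carry two targets.
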